- 10. Subjects who have a history of a psychological illness or condition that would interfere with their ability to understand and follow the requirements of the study.
- 11. Subjects who have undergone recent facial surgery.
- 12. Subjects currently participating in any other clinical trial.
- 13. Subjects having started hormone replacement therapies (HRT) or hormones for birth control less than 3 months prior to the study entry; or who plan on starting, stopping or changing doses of HRT or hormones for birth control during the study.
- 14. Subjects who have a cardiac pacemaker, implanted defibrillator, or other implanted metallic or electronic device.
- 15. Subjects who are wearing EKG monitoring equipment.
- 16. Subjects with phlebitis, thrombophlebitis, broken capillaries, or varicose veins.
- 17. Subjects who have seizures, epilepsy, or cancer/tumors.
- 18. Subjects who have a history of hypertrophic scarring or keloid formation.

Endpoints:

Tolerability Endpoint:

The tolerability endpoint is the investigator-assessed absence of skin irritation from the facial study device at any time during the 12-week study.

Safety Endpoint:

The safety endpoint is the overall incidence of all adverse events reported during the study.

Efficacy Endpoint: The efficacy endpoint is the investigator assessed improvement in investigator global assessment (IGA) after 12 weeks of every other day device use as compared to baseline.

Measures:

Dermatologist Investigator assessed efficacy parameters: Investigator global acne assessment (IGA) based on the following 5 point ordinal scale: 0=clear, 1=almost

clear, 2=mild, 3=moderate, and 4=severe. IGA assessments will be conducted at baseline, week 2, week 4, week 8, and week 12.

Dermatologist Investigator lesion counts: inflammatory lesion count (papules, pustules), non-inflammatory lesion count (open comedones, closed comedones). Lesion counts will be conducted at baseline, week 2, week 4, week 8, and week 12.

Dermatologist Investigator assessed tolerability parameters: peeling, dryness, redness, and swelling. All assessments will be made on a 5-point ordinal scale (0=none, 1=minimal, 2=mild, 3=moderate, & 4=severe) at baseline, week 2, week 4, week 8, and week 12.

Self-assessment questionnaire: To be provided by sponsor. All assessments will be at week 2, week 4, and week 8, and week 12.

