2. STUDY VISIT SCHEDULE

| | Visit 1 | Visit 2 | Visit 3 | Visit 4 | Visit 5 |
|--|---------|-----------|-----------|-----------|------------|
| Procedures | BL | Week 2 | Week 4 | Week 8 | Week 12 |
| Informed Consent Procedure | X | | | | |
| Inclusion/Exclusion Criteria | X | | | | |
| Brief Medical History and Concomitant Medications Review | X | X | X | X | X |
| Investigator Clinical Grading for Tolerability | X | X | X | X | X |
| Investigator Clinical Facial Grading (IGA) | X | X | X | X | X |
| Investigator Acne Lesion Counts | X | X | X | X | X |
| Subject Clinical Grading for Tolerability | X | X | X | X | X |
| Subject Self Assessment Questionnaire | | X | X | X | X |
| Photography | X | X | X | X | X |
| Dispense electroconductive media | X | X | X | X | |
| Device Check/Dispensing | X | X | X | X | |
| Subject Diary Assessment and Compliance Check | | X | X | X | X |
| Subject Device Accountability and Study Completion | | | | | X |

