5. STUDY DESIGN OVERVIEW

Male and female subjects will be enrolled in this single-site monadic study to evaluate the effect of a direct-current device on acne treatment. Subjects who sign the consent form and meet all inclusion criteria and none of the exclusion criteria will be enrolled at the baseline visit. Subjects will be asked to continue their self-selected moisturizer, non-medicated cleanser, and sunscreen they have used without difficulty for the prior 30 days and for the 12 week study. Subjects must also continue all facial products and cosmetics unchanged for the duration of the study. No other oral or topical acne products can be used. Subjects must be washed out of all topical acne products for at least 2 weeks and all oral acne products for at least 4 weeks. Subjects must possess mild to moderate acne with 5-30 inflammatory lesions and no nodules/cysts.

At baseline visit, subjects will receive the study acne device to be applied to the areas of the face afflicted by acne following cleansing, every other day. The dermatologist investigator will assess the face for the investigator global acne assessment (IGA) based on the following 5 point ordinal scale: 0=clear, 1=almost clear, 2=mild, 3=moderate, and 4=severe. In addition, the dermatologist investigator will perform an inflammatory and non-inflammatory lesion count. The dermatologist investigator will assess the tolerability of the device in terms of peeling, dryness, redness, and swelling on a 5-point ordinal scale (0=none, 1=minimal, 2=mild, 3=moderate, & 4=severe).

The subjects will assess device tolerability in terms of itching, burning, redness, and swelling. All assessments will be made on a 5-point ordinal scale (0=none, 1=minimal, 2=mild, 3=moderate, & 4=severe). Subjects will be given their diaries, study device, and electroconductive media and asked to return to the research center in 2 weeks. A reminder text will be sent to encourage compliance prior to the week 2 visit.

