6.3 INCLUSION CRITERIA

The following items represent the inclusion criteria:

- 1. Subjects with mild to moderate acne (5-30 inflammatory lesions and no nodules/cysts).
- 2. Male and female subjects age 18-50 years.
- 3. Subjects with all Fitzpatrick skin types.
- 4. Subjects of all complexion types (normal, oily, dry, combination).
- 5. Subjects who have used the same moisturizer without difficulty for 30 days and will continue using same moisturizer during the 12 week study.
- 6. Subjects agree not to introduce any new colored cosmetics (lipsticks, eye shadows, facial foundations, blush, & powder).
- 7. Subjects who are using no other acne products for the duration of the study.
- 8. No known medical conditions that, in the investigator's opinion, may interfere with study participation.
- 9. Women of childbearing potential must be willing to use a form of birth control during the study. For the purpose of this study, the following are considered acceptable methods of birth control: oral contraceptives, Norplant®, Depo-Provera®, double barrier methods (e.g., condom and spermicide) and abstinence.
- 10. Subjects have signed an Informed Consent Form in compliance with 21CFR, Part 50: "Protection of Human Subjects."
- 11. Subjects are dependable and able to follow directions and willing to comply with the schedule of visits.

12. Subjects in generally good physical and mental health.

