All investigator selected subjects will be photographed with the Canfield VISIA CR using Standard 1 lighting at baseline, week 2, week 4, and week 8, and week 12.

7.2.4 WEEK 8

At the week 8 visit, the dermatologist investigator will assess the face for the investigator global acne assessment (IGA) based on the following 5 point ordinal scale: 0=clear, 1=almost clear, 2=mild, 3=moderate, and 4=severe. In addition, the dermatologist investigator will perform an inflammatory and

noninflammatory lesion count within each facial quadrant. The study device will be inspected for proper operation and the study diary will be inspected for compliance.

The dermatologist investigator will assess the tolerability of the device in terms of peeling, dryness, redness, and swelling on a 5-point ordinal scale (0=none, 1=minimal, 2=mild, 3=moderate, and 4=severe). The subjects will then assess device tolerability in terms of itching, burning, redness, and swelling. All assessments will be made on a 5-point ordinal scale (0=none, 1=minimal, 2=mild, 3=moderate, and 4=severe). The subjects will also complete a sponsor provided marketing questionnaire. Subjects will be asked to return to the research center at week 12. A reminder text will be sent to encourage compliance prior to the week 12 visit.

All investigator selected subjects will be photographed with the Canfield VISIA CR using Standard 1 lighting at baseline, week 2, week 4, and week 8, and week 12.

7.2.5 WEEK 12

At the week 12 visit, the dermatologist investigator will assess the face for the investigator global acne assessment (IGA) based on the following 5 point ordinal scale: 0=clear, 1=almost clear, 2=mild, 3=moderate, and 4=severe. In addition, the dermatologist investigator will perform an inflammatory and noninflammatory lesion count within each facial quadrant. The study device will be inspected for proper operation and the study diary will be inspected for compliance. The diary and the study materials will be collected.

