12. STATISTICAL METHODS

The statistical evaluation will be performed by Dermatology Consulting Services. Along with descriptive statistics (means, standard deviations and percentages), investigator and subject ordinal nonparametric data will be analyzed using the Wilcoxon signed rank test. Acne lesion counts will be assessed using a Student t test. Change will be considered significant at a p value of less than or equal to 0.05.

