12.5 EFFICACY ASSESSMENT

The efficacy endpoint is the investigator assessed improvement in investigator global assessment (IGA) after 12 weeks of every other day device use as compared to baseline.

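### The repeated lesion counts omit nodules and cysts, so a papule or pustule that progresses to one lowers the inflammatory count: a small, one-directional error in a supporting measure

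*Combined protocol and SAP*

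**What the plan says.** The Measures part of the synopsis (section 1) holds the only definition of the counts: "inflammatory lesion count (papules, pustules), non-inflammatory lesion count (open comedones, closed comedones". The timing follows: "Lesion counts will be conducted at baseline, week 2, week 4, week 8, and week 12".

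Nodules and cysts appear only where the population and eligibility are described. Inclusion criterion 1 in section 6.3 reads "Subjects with mild to moderate acne (5-30 inflammatory lesions and no nodules/cysts", and section 5 repeats it: "Subjects must possess mild to moderate acne with 5-30 inflammatory lesions and no nodules/cysts". This wording names nodules and cysts apart from the inflammatory lesions that are counted.

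Sections 7.2.1 to 7.2.5 have the investigator "perform an inflammatory and noninflammatory lesion count within each facial quadrant" at each visit. The schedule in section 2 has a single row for this, "Investigator Acne Lesion Counts". Neither place gives a field or rule for a nodule or cyst that appears after baseline.

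Section 12 states the analysis: "Acne lesion counts will be assessed using a Student t test". The named endpoint is a different variable. Section 12.5 says: "The efficacy endpoint is the investigator assessed improvement in investigator global assessment (IGA) after 12 weeks".

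**The concern.** A lesion count should not fall when a lesion gets worse. Under the written definition, a papule or pustule that becomes a nodule or cyst leaves the inflammatory count and goes nowhere else, so the t test receives a decrease. A nodule arising on clear skin registers as no change. One arising from a comedone lowers the non-inflammatory count and leaves the inflammatory count as it was.

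Every subject uses the active device (section 10.6), so there is no concurrent arm in which the same misclassification could cancel. The cover page mentions a historical control, but the documents say nothing about how lesions were counted in it.

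What is at stake is the credibility of the supporting lesion-count result and a clear record of the most severe kind of lesion worsening.

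**Working it through.** The plan offers no figure to reproduce on this point. Its one design number, 50 subjects, is given in section 12.1 without an effect size, standard deviation (SD), power or dropout rate.

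**Inputs from the documents**
- Counted lesions: papules and pustules; open and closed comedones (synopsis, Measures).
- Baseline: 5 to 30 inflammatory lesions, no nodules or cysts (section 6.3, item 1).
- Sample size: 50, single arm (sections 6.1 and 10.6).
- Test: Student t test on counts (section 12), two-sided at 0.05 (section 12.2).

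**Assumptions**
- The number of conversions. The documents give no progression rate.
- The SD of change in the inflammatory count, taken as 3, 5 or 8 lesions.
- A paired (one-sample) test of change from baseline. The plan does not specify the form.

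**Step 1: direction.** Let K be the number of nodules and cysts present at a visit. K is 0 at baseline by eligibility and cannot be negative later. Then

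recorded change in inflammatory count = change in the total including nodules/cysts − K.

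The recorded change is never less favourable than the change in the full total. The error has one direction, provided the counts follow the written definition.

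**Step 2: one subject, one conversion, no other change.** Apparent reduction = 1 / baseline count.
- Baseline 5: 1/5 = 20%. With two conversions, 2/5 = 40%.
- Baseline 15: 1/15 = 6.7%.
- Baseline 30: 1/30 = 3.3%.

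**Step 3: group mean.** With m conversions in 50 subjects, the shift in mean change is −m/50.
- m = 1: −0.02 lesion.
- m = 5: −0.10.
- m = 10: −0.20.
- m = 25: −0.50.

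**Step 4: effect on the test.** With n = 50, the result is significant when the mean change exceeds t(0.975, 49)/√50 = 2.0096/7.0711 = 0.2842 SD. The conversions needed to put the mean at that threshold, with no other change, are 0.2842 × SD × 50. The last two columns give the chance of a significant result in the device's favour from the noncentral t distribution, with nothing but the conversions shifting the mean. The nominal value is 2.5%.

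| Assumed SD | Threshold mean change | Conversions needed | 5 conversions | 10 conversions |
|---|---|---|---|---|
| 3 | 0.85 | about 43 | 4.19% | 6.71% |
| 5 | 1.42 | about 71 | 3.43% | 4.62% |
| 8 | 2.27 | about 114 | 3.05% | 3.70% |

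**Step 5: after the change.** If nodules/cysts are in the inflammatory total, a conversion changes it by 0 instead of −1, and a nodule arising on clear skin or from a comedone changes it by +1.

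**The case against.** The strongest reply is that this touches a supporting measure in a population where nodules may be rare, and that other parts of the plan would show them. Much of that stands.

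- **Endpoint.** The efficacy endpoint is the IGA, graded at every visit on a scale that runs to severe. The investigator can grade a subject with a new nodule as worse. The grades are bare labels, so nothing obliges this, but a reader who infers that the efficacy endpoint scores such a subject as improved goes beyond the text.
- **Safety.** A reader might also infer that new nodules would go untabulated. Section 11.2 defines adverse experiences broadly enough to include them, and section 12.4 has all adverse events summarized and grouped by relation to product. What remains is that nodules are not named, nothing requires worsening acne to be logged as an adverse experience, and an entry there does not alter the count.
- **Sign.** It is tempting to say that the subjects who worsen most are scored as improved. That holds only if a conversion is not offset by new papules or pustules; a worsening subject may gain those, and the count then rises. The documents do not show which pattern to expect.
- **Silence.** The plan does not expressly tell the investigator to drop nodules, and one might be counted as inflammatory in practice. Nothing written supports that, and unwritten handling could vary from visit to visit.
- **Remedy.** Adding nodules to the total only makes a conversion neutral. This is correct, and it is why the separate report is needed as well.

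**Conclusion.** The point holds at low severity. Followed as written, the count definition can move the lesion-count result only toward the device, and the single-arm design has nothing to offset it. At an assumed 5 conversions in 50 subjects, the mean shifts by 0.1 lesion, and the chance of a false favourable result rises from 2.5% to between 3.05% and 4.19% across the assumed SDs. Conversions alone would have to total roughly 43 to 114 to bring the mean to the significance threshold, so this is not a case for expecting a reversed trial result. The distortion can be marked for one subject with few lesions: 20% at a baseline of 5 with no other change, against 3.3% at 30.

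These figures rest on literal use of the definition, a paired test, and assumed conversion numbers and SDs. The direction of the error rests only on the definition and on the entry requirement of no nodules or cysts.

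**What to change.** Amend the Measures text in the synopsis and sections 7.2.1 to 7.2.5, before the data are analysed, as follows:

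1. The investigator records nodules/cysts as a separate count at every visit, by quadrant as for the other lesions. The baseline value is 0 for every eligible subject.
2. The inflammatory total is papules plus pustules plus nodules/cysts, so that a conversion is not scored as a reduction. Eligibility counts and baseline totals do not change.
3. The report gives, by visit, the number of subjects with any new nodule or cyst. This is the part that makes worsening visible.

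The cost is up to four extra fields per visit, or 4 × 5 = 20 per subject over the five visits. They are completed in the same examination by the same investigator, with no added visit or staff.

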2. STUDY VISIT SCHEDULE

| | Visit 1 | Visit 2 | Visit 3 | Visit 4 | Visit 5 |
|--|---------|-----------|-----------|-----------|------------|
| Procedures | BL | Week 2 | Week 4 | Week 8 | Week 12 |
| Informed Consent Procedure | X | | | | |
| Inclusion/Exclusion Criteria | X | | | | |
| Brief Medical History and Concomitant Medications Review | X | X | X | X | X |
| Investigator Clinical Grading for Tolerability | X | X | X | X | X |
| Investigator Clinical Facial Grading (IGA) | X | X | X | X | X |
| Investigator Acne Lesion Counts | X | X | X | X | X |
| Subject Clinical Grading for Tolerability | X | X | X | X | X |
| Subject Self Assessment Questionnaire | | X | X | X | X |
| Photography | X | X | X | X | X |
| Dispense electroconductive media | X | X | X | X | |
| Device Check/Dispensing | X | X | X | X | |
| Subject Diary Assessment and Compliance Check | | X | X | X | X |
| Subject Device Accountability and Study Completion | | | | | X |

3. INTRODUCTION

Acne is a disease that affects individuals of all ages. 85% of Americans 12-24 years of age have acne and epidemiological studies show a similar prevalence in other countries. The etiology of acne is multifaceted, involving abnormal follicular hyperkeratizination, increased sebum production; follicular colonization by *C. acnes*, and inflammation. Hyperkeratinization induced microcomedone formation is the first step in acne lesion formation. As keratinocytes and sebum continue to accumulate, a visible non-inflammatory comedone lesion forms. The continued proliferation of *C. acnes* within the follicle results in follicular wall rupture and eventual formation of an inflammatory papule or pustule. Successful treatment of acne involves interrupting this sequence of events. This research examines the ability of a novel device to treat acne.

4. STUDY OBJECTIVE

The objective of this study is demonstrate the safety and efficacy of a novel direct current device in the treatment of mild to moderate inflammatory acne after 12 weeks of every other day use.

5. STUDY DESIGN OVERVIEW

Male and female subjects will be enrolled in this single-site monadic study to evaluate the effect of a direct-current device on acne treatment. Subjects who sign the consent form and meet all inclusion criteria and none of the exclusion criteria will be enrolled at the baseline visit. Subjects will be asked to continue their self-selected moisturizer, non-medicated cleanser, and sunscreen they have used without difficulty for the prior 30 days and for the 12 week study. Subjects must also continue all facial products and cosmetics unchanged for the duration of the study. No other oral or topical acne products can be used. Subjects must be washed out of all topical acne products for at least 2 weeks and all oral acne products for at least 4 weeks. Subjects must possess mild to moderate acne with 5-30 inflammatory lesions and no nodules/cysts.

At baseline visit, subjects will receive the study acne device to be applied to the areas of the face afflicted by acne following cleansing, every other day. The dermatologist investigator will assess the face for the investigator global acne assessment (IGA) based on the following 5 point ordinal scale: 0=clear, 1=almost clear, 2=mild, 3=moderate, and 4=severe. In addition, the dermatologist investigator will perform an inflammatory and non-inflammatory lesion count. The dermatologist investigator will assess the tolerability of the device in terms of peeling, dryness, redness, and swelling on a 5-point ordinal scale (0=none, 1=minimal, 2=mild, 3=moderate, & 4=severe).

The subjects will assess device tolerability in terms of itching, burning, redness, and swelling. All assessments will be made on a 5-point ordinal scale (0=none, 1=minimal, 2=mild, 3=moderate, & 4=severe). Subjects will be given their diaries, study device, and electroconductive media and asked to return to the research center in 2 weeks. A reminder text will be sent to encourage compliance prior to the week 2 visit.

Subjects will return to the research center at week 2, week 4, and week 8 for the same study activities as conducted at baseline. However, in addition, a subject self-assessment marketing questionnaire provided by the sponsor will be administered. Subject diaries will be checked at each return visit for compliance and completion. Subjects will be redispensed electroconductive media gel at each visit and the devices will be inspected for any problems. Reminder texts will be sent prior to each visit to encourage compliance.

Subjects will return to the research center at week 12 for the same study activities as conducted at baseline. Study diaries and devices will be checked and collected. Subjects will terminate their study participation at this time.

20 investigator selected subjects will be photographed with the Canfield VISIA CR using Standard 1 lighting at baseline, week 2, week 4, and week 8, and week 12.

6. STUDY POPULATION

6.1 NUMBER OF SUBJECTS

50 subjects enrolled

6.2 SUBJECT CHARACTERISTICS

Healthy male and female subjects 18-50 years of age of all Fitzpatrick skin types with mild to moderate acne consisting of 5-30 inflammatory lesions and no nodules/cysts

6.3 INCLUSION CRITERIA

The following items represent the inclusion criteria:

- 1. Subjects with mild to moderate acne (5-30 inflammatory lesions and no nodules/cysts).
- 2. Male and female subjects age 18-50 years.
- 3. Subjects with all Fitzpatrick skin types.
- 4. Subjects of all complexion types (normal, oily, dry, combination).
- 5. Subjects who have used the same moisturizer without difficulty for 30 days and will continue using same moisturizer during the 12 week study.
- 6. Subjects agree not to introduce any new colored cosmetics (lipsticks, eye shadows, facial foundations, blush, & powder).
- 7. Subjects who are using no other acne products for the duration of the study.
- 8. No known medical conditions that, in the investigator's opinion, may interfere with study participation.
- 9. Women of childbearing potential must be willing to use a form of birth control during the study. For the purpose of this study, the following are considered acceptable methods of birth control: oral contraceptives, Norplant®, Depo-Provera®, double barrier methods (e.g., condom and spermicide) and abstinence.
- 10. Subjects have signed an Informed Consent Form in compliance with 21CFR, Part 50: "Protection of Human Subjects."
- 11. Subjects are dependable and able to follow directions and willing to comply with the schedule of visits.

12. Subjects in generally good physical and mental health.

